9.1.7 History of Present Illness

A present illness refers to any clinically significant disease or symptom existing at the first vaccination with study drug. All clinically significant laboratory values and abnormal findings observed during examination prior to vaccination with the study drug should be regarded as present illnesses. The details of present illnesses (diagnoses) should be recorded.

9.1.8 Contraception and Pregnancy Avoidance Procedure

From signing of informed consent, throughout the duration of the study, and for 12 weeks after last dose of study drug, female subjects of childbearing potential* who are sexually active with a nonsterilized male partner** must use adequate contraception. In addition they must be advised not to donate ova during this period.

*A woman is considered a woman of childbearing potential (WOCBP), i.e. fertile, following menarche and until becoming post-menopausal unless permanently sterile. Permanent sterilization methods include hysterectomy, and bilateral oophorectomy. A postmenopausal state is defined as no menses for 12 months without an alternative medical cause. A high follicle stimulating hormone (FSH) level in the postmenopausal range (FSH >40 IU/L) may be used to confirm a post-menopausal state in younger women (e.g. those < 45 year old) or women who are not using hormonal contraception or hormonal replacement therapy. However, in the absence of 12 months of amenorrhea, a single FSH measurement is insufficient.

**Sterilized males should be at least 1 year post vasectomy and have confirmed that they have obtained documentation of the absence of sperm in the ejaculate or have had bilateral orchidectomy.

Such subjects will be provided with information on acceptable methods of contraception as part of the subject informed consent process, and will be asked to sign a consent form stating that they understand the requirements for avoidance of pregnancy during the course of the study.

During the course of the study, regular urine human chorionic gonadotropin (hCG) pregnancy tests will be performed only for women of childbearing potential and subjects will receive continued guidance with respect to the avoidance of pregnancy as part of the study procedures [Appendix A](#) In addition to a urine hCG pregnancy test before vaccination on the day of vaccination with the study drug (Day 1), the result of urine hCG test at the end of study (or discontinuation) (Day 43) must be confirmed negative.

In this study, the only acceptable methods of contraception are:

Barrier methods (each time the subject has intercourse):

- Male condom PLUS spermicide.
- Copper T PLUS condom.
- Progesterone T PLUS condom.

Hormonal contraceptives:

- Combined pill.

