7.5 Criteria for Discontinuation or Withdrawal of a Subject

The primary reason for discontinuation or withdrawal of the subject from the study or study drug should be recorded in the case report form ([e]CRF) using the following categories. For subjects who discontinue/is withdrawn before enrollment in this study, see [9.1.12](#)

1. Death

The subject dies during the study.

Note: If the subject dies on study, the event will be considered as a serious adverse event (SAE). See Section [10.2.2](#) for the reporting procedures.

2. Adverse event (AE)

The subject has experienced an AE that requires early termination because continued participation imposes an unacceptable risk to the subject's health or the subject is unwilling to continue because of the AE.

3. Protocol deviation

The discovery after enrollment that the subject failed to meet protocol entry criteria or did not adhere to protocol requirements, and continued participation poses an unacceptable risk to the subject's health.

4. Lost to follow-up

The subject did not return to the clinic and attempts to contact the subject were unsuccessful. Attempts to contact the subject must be documented in the subject's source documents.

5. Withdrawal by the subject

The subject wishes to be withdrawn from the study. The reason for withdrawal, if provided, should be recorded in the (e)CRF.

Note: All attempts should be made to determine the underlying reason for the withdrawal and, where possible, the primary underlying reason should be recorded. In the case of withdrawal due to an AE, however, consideration should be given to classifying it as "AE(s)" rather than as "voluntary withdrawal by the subject."

6. Study Terminated by sponsor.

The sponsor terminates the study.

7. Pregnancy

The subject is found to be pregnant.

Note: If the subject is found to be pregnant, the subject must be withdrawn from the study immediately. The procedure is described in Section [9.1.9](#).

8. Other

CONFIDENTIAL

Note: The specific reasons should be recorded in the “specify” field of the (e)CRF.

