8.1.3 Dose and Regimen

According to the following procedures, two doses of the study drug 0.5 mL will be injected into the brachial muscle (deltoid muscle) on Days 1 and 22.

- Let the study drug (vial) warm to room temperature.
- Prior to administration, shake the vial for 5-10 seconds to mix the vaccine suspension completely.
- Prior to administration, visually inspect for any insoluble particulate matter or discoloration. The study drug should not be used if any insoluble particulate matter, discoloration, or leakage is observed.
- Using a 1-inch long, 25-gauge needle, inject a dose of 0.5 mL into the arm opposite to the one used for blood collection to obtain a sample for immunogenicity testing wherever possible.
- The following should be noted to avoid the effect of intramuscular vaccination on the tissues and nerves:
- Injecting into a nerve tract should be avoided.
- In the case of intense pain and/or backflow of blood associated with needle insertion, withdraw the needle immediately and inject into another site.

CONFIDENTIAL

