9.1.9 Pregnancy

If any subject is found to be pregnant during the study she should be withdrawn and any sponsor-supplied drug should be immediately discontinued.

If the pregnancy occurs during administration of active study drug, eg, after Day 1 or within 12 weeks of the last dose of active study drug, the pregnancy should be reported immediately, using a pregnancy notification form, to the contact listed on the attached sheet.

If the female subject agrees to the primary care physician (obstetrician) being informed, the investigator should notify the primary care physician that the subject was participating in a clinical study at the time she became pregnant and provide details of treatment the subject received.

All pregnancies in subjects on active study drug including comparator will be followed up to final outcome, using the pregnancy form. Pregnancies will remain blinded to the study team. The outcome, including any premature termination, must be reported to the sponsor. An evaluation after the birth of the child will also be conducted.

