From Days 8 to 22 (before visiting the study site), subjects will measure their body temperature (oral) only if they develop pyrexia (or any symptoms suggestive of pyrexia) (see Section [9.1.11](#)).
- Supply of the subject diary
 - Time point: Day 1 (Diaries 1 and 2) (Diaries 3 and 4 may be supplied on Day 1)
- Completion of the subject diary (by subjects)
 - Time points: From Day 1 (after the initial vaccination) to Day 7 (Diary 1) and from Day 8 to Day 22 (before visiting the study site) (Diary 2)

During the periods from Day 1 (after the completion of study visit) to Day 7 and from Day 8 to Day 22 (before visiting the study site), subjects will monitor for and record any systemic reactions, injection site reactions, etc. (see Section [9.1.11](#)).

9.3.3 <Treatment Period/Day 22 (Starting before the Second Vaccination and Ending after the Completion of the Second Vaccination)>

The following tests, observations, and assessments will be performed on Day 22 (starting before the second vaccination and ending after the completion of the second vaccination).

- Physical Examination
- Vital signs (body temperature [oral], blood pressure, and pulse and respiratory rates)
- Collection of concomitant medications and AEs
- Blood sampling for the immunogenicity evaluation
- Collection of the subject diary (Diaries 1 and 2)

Subjects will receive vaccination with the study drug under the supervision of the investigator at the study site.

9.3.4 <Treatment Period/Day 22 (after the Second Vaccination) to Day 43 (before Visiting the Study Site)>

During the period from Day 22 (after the second vaccination) to Day 43 (before visiting the study site), the following testing, observation, and assessments will be performed: Subjects will monitor themselves at home during the period after the completion of Day 22 visit until before Day 43 visit (see Section 9.1.11).

- Physical Examination
 - Time point: Day 22 (after vaccination)
The investigator will monitor for any acute hypersensitivity reaction, etc., for 30 minutes after vaccination.
- Vital signs (blood pressure and pulse and respiratory rates)
 - Time point: Day 22 (after vaccination)
Vital signs will be measured 30 minutes after vaccination.
- Vital signs (body temperature [oral])
 - Form Days 22 to 28, subjects will measure their body temperature (oral) and record it in the subject diary.

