10.1.3 SAEs

An SAE is defined as any untoward medical occurrence in a clinical investigation subject administered a pharmaceutical product (including a study drug), which:

1. Results in DEATH.
2. Is LIFE THREATENING.
 - The term "life threatening" refers to an event in which the subject was at risk of death at the time of the event; it does not refer to an event that hypothetically might have caused death if it were more severe.
3. Requires inpatient HOSPITALIZATION or prolongation of existing hospitalization.
4. Results in persistent or significant DISABILITY/INCAPACITY.
5. Leads to a CONGENITAL ANOMALY/BIRTH DEFECT.
6. Is an IMPORTANT MEDICAL EVENT that satisfies any of the following:
 - May require intervention to prevent items 1 through 5 above.
 - May expose the subject to danger, even though the event is not immediately life threatening or fatal or does not result in hospitalization.
 - Includes any event or synonym described in the Takeda Medically Significant AE List ([Table 10.a](#)).

Table 10.a Takeda Medically Significant AE List

Term	
Acute respiratory failure/acute respiratory distress syndrome	Acute liver failure
Torsade de pointes / ventricular fibrillation / ventricular tachycardia	Anaphylactic shock
Malignant hypertension	Acute renal failure
Convulsive seizure (including seizure and epilepsy)	Pulmonary hypertension
Agranulocytosis	Pulmonary fibrosis (including interstitial lung disease)
Aplastic anemia	Confirmed or suspected endotoxin shock
Toxic epidermal necrolysis/Stevens-Johnson syndrome	Confirmed or suspected transmission of infectious agent by a medicinal product
Hepatic necrosis	Neuroleptic malignant syndrome / malignant hyperthermia
	Spontaneous abortion / stillbirth and fetal death

Note: The terms listed in this table may be “important medical events” that require the reporting of SAEs and are therefore broadly defined medical terms.

7. The following important medical events associated with the use of an influenza vaccine: neuritis, encephalitis, vasculitis, Guillain-Barre syndrome, Bell’s palsy (facial palsy), and demyelinating disorder (including acute disseminated encephalomyelitis [ADEM] and multiple sclerosis)

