Appendix A Schedule of Study Procedures

	Screening		Treatment			
	Visit number	Visit 1		Visit 2		Visit 3/at discontinuation ¹²⁾
Day ¹⁾		1	1 to 22	22	22 to 43	43/-
Days after the initial vaccination		0	0 to 21	21	21 to 42	42 (Visit 2 + 21)/-
Acceptable time window for visit (day)		-	-	+0 to 2	-	Visit 2 + 19 to Visit 2 + 23 /date of discontinuation + 28
	Pre-vaccination	Post-vaccination		Pre-vaccination	Post-vaccination	
Informed Consent	X ²⁾					
Demographics	X					
Past history, present illness, and prior treatments	X ³⁾					
Height and weight	X					
Vital signs (blood pressure and pulse and respiratory rates)	X	X ⁴⁾		X	X ⁴⁾	X ⁵⁾
Vital signs (body temperature [oral])	X		X ^{6) 7)}	X		X ^{6) 7)}
Pregnancy test ⁹⁾	X					X
Physical examination	X	X ⁹⁾		X	X ⁹⁾	X
Eligibility assessment	X					
Enrollment	X					
Blood sampling (immunogenicity evaluation) ¹⁰⁾	X			X		X
Vaccination with the study drug	X			X		
Diaries 1 and 2		To be provided	To be recorded	To be collected		(To be collected, if not yet collected)
Diaries 3 and 4					To be provided ¹¹⁾	To be recorded
Adverse events		←			→	
Concomitant medications	←				→	

- 1) The day before vaccination with the study drug is defined as Day -1, and the day of vaccination with the study drug (Visit 1) is defined as Day 1.
- 2) Informed consent must be obtained before any study procedure is performed. Informed consent is considered valid if it is obtained within 28 days prior to Visit 1 (Day -28).
- 3) Prior treatments include those given before signing the informed consent form, and past history and present illness include those occurring before the first vaccination of study drug.
- 4) On the day of vaccination with study drug, blood pressure, pulse rate, and respiratory rate will be measured before vaccination and approximately 30 minutes after vaccination.
- 5) No respiratory rate measurement will be required at Day 43 and at discontinuation.
- 6) Among vital signs, body temperature will be measured by each subject every day in the evening wherever possible for 7 days after vaccination (after vaccination on Day 1 until Day 7 and after vaccination on Day 22 until Day 28) and be recorded in the diary provided to each subject.

CONFIDENTIAL

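### No pregnancy test is scheduled before the second vaccination on Day 22, the only dose the pregnancy stop rule can still prevent after Day 1

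*Protocol*

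**What the plan says.** - **Dosing.** Section 8.1.3: "two doses of the study drug 0.5 mL will be injected into the brachial muscle (deltoid muscle) on Days 1 and 22".
- **Stop rules.** Section 7.5, item 7: "If the subject is found to be pregnant, the subject must be withdrawn from the study immediately". Section 9.1.9: "If any subject is found to be pregnant during the study she should be withdrawn and any sponsor-supplied drug should be immediately discontinued".
- **Tests named.** Section 9.1.8 gives the first test ("In addition to a urine hCG pregnancy test before vaccination on the day of vaccination with the study drug (Day 1") and then adds that "the result of urine hCG test at the end of study (or discontinuation) (Day 43) must be confirmed negative". The same paragraph speaks of *regular* testing, but refers to Appendix A for the schedule.
- **Visit lists.** A pregnancy test is listed in Sections 9.3.1 (Day 1), 9.3.5 (Day 43) and 9.3.6 (discontinuation). Section 9.3.3 opens with "The following tests, observations, and assessments will be performed on Day 22 (starting before the second vaccination" and then lists physical examination, vital signs, concomitant medications and AEs, the immunogenicity blood sample and diary collection. It lists no pregnancy test, and neither does Section 9.3.4.
- **Appendix A.** The pregnancy-test row is marked at Visit 1 before vaccination and at Visit 3 or discontinuation only. Visit 2 falls 21 days after Visit 1, with a window of +0 to 2 days. The Visit 3 window is "Visit 2 + 19 to Visit 2 + 23".

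**The concern.** Once dose 1 has been given, the instruction to stop study drug can act on one thing only: dose 2. For a subject who completes the study, the sole scheduled test after baseline comes once both doses are in. It can start reporting and follow-up, but it cannot prevent an exposure. The test at discontinuation does not help here, because a woman who has discontinued is no longer due dose 2.

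A pregnancy too early to show on Day 1, or conceived soon after, could come to light before dose 2 only through self-report, the general AE question (Section 10.2.1.2), diary review, the physical examination or an unscheduled test. None of these is aimed at pregnancy.

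The protocol treats exposure in pregnancy as something to avoid and to follow. Exclusion criterion 20 bars pregnant women, Section 9.1.8 requires contraception until 12 weeks after the last dose, and Section 9.1.9 follows pregnancies to outcome. Table 10.a in Section 10.1.3 lists "Spontaneous abortion / stillbirth and fetal death" among medically significant events. Section 4.2 also says there is no clinical experience with vaccine made from an attenuated strain, which is the product used here.

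**Working it through.** The plan gives no figure to reproduce. The check is a comparison of the schedule with the stop rule, followed by a simple calculation of the gap.

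**1. Schedule against rule (a woman who completes the study)**

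| Time point | Dose | Scheduled urine hCG | Doses still to come |
|---|---|---|---|
| Visit 1 (Day 1), before vaccination | 1 | Yes | 2 |
| Visit 2 (Day 22), before vaccination | 2 | No | 1 |
| Visit 3 (Day 43) | none | Yes | 0 |

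The blank at Visit 2 is not a table-reading problem. The blood-sampling and vital-sign rows of Appendix A do carry Visit 2 marks, and the text list in Section 9.3.3 agrees with the blank.

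**2. Intervals, from the Appendix A windows**

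- Last test to dose 2: g = 21 + 0 to 21 + 2 = 21 to 23 days.
- Visit 2 to Visit 3: 19 to 23 days.
- First test to second test: 21 + 19 = 40 days to 23 + 23 = 46 days (nominal 21 + 21 = 42).

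**3. Conception dates left uncovered before dose 2**

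Let L be the number of days from conception to a positive urine test. The documents give no value, so L is an assumption: 10 to 14 days as the main range, 7 to 21 as a wider one.

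- The Day 1 test misses any conception later than L days before Day 1. Dose 2 follows g days after Day 1, so the uncovered dates span g + L days.
- A test at Visit 2 reveals conceptions up to L days before dose 2. The uncovered span falls to L days, so the test closes g days.
- Share closed = g / (g + L).

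| L (assumed) | g = 21 | g = 23 |
|---|---|---|
| 7 | 21/28 = 75% | 23/30 = 77% |
| 10 | 21/31 = 68% | 23/33 = 70% |
| 14 | 21/35 = 60% | 23/37 = 62% |
| 21 | 21/42 = 50% | 23/44 = 52% |

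For L of 10 to 14 days, the uncovered span today is 31 to 37 days. A Visit 2 test closes 21 to 23 of them and leaves 10 to 14.

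**4. What cannot be computed**

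The expected number of affected women needs the number of women of childbearing potential and a pregnancy rate. The documents give neither. The percentages above are shares of calendar dates, not probabilities of pregnancy or exposure.

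**The case against.** The strongest reply is that testing is only a back-up and the main control is already strong. Exclusion criterion 20 removes women who wish to become pregnant up to 12 weeks after the last dose. Inclusion criterion 5 requires agreement to contraception. Section 9.1.8 restricts the acceptable methods, requires signed understanding and promises continuing guidance. This stands, and it is why the number affected is probably small. But the protocol tests on Day 1 and Day 43 despite these controls, so it does not rely on contraception alone.

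A second reply is that evidence of harm is thin. The vaccine is inactivated and given by its approved regimen. Section 4.1.1 sees no specific risk. Table 10.a is a general sponsor list, and parts of Section 9.1.9 read as template text, with mentions of a comparator and blinding. This also stands as to weight. It does not explain why a rule to stop dosing has no scheduled test before the one dose it can stop.

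A third reply is that there is no literal contradiction: the stop rules apply when a pregnancy is found, and neither promises a test before each dose. They also require withdrawal, and Section 9.1.9 adds reporting and follow-up, which a Day 43 test serves. That is correct. The point is a gap between intent and schedule, not an inconsistency of wording. The word *regular* in Section 9.1.8 does not fill it, because Appendix A adds no test at Visit 2.

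Finally, the share of dates closed depends on an assumed lag and says nothing about frequency. Agreed; it shows only how much of the gap a test can cover.

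**Conclusion.** The concern holds. The protocol schedules no pregnancy test before dose 2, so its own instruction to stop vaccination on pregnancy has no scheduled trigger at the only time it could still withhold a dose. This rests on the protocol text and needs no assumption.

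The gap from the last test to dose 2 is 21 to 23 days. With an assumed detection lag of 10 to 14 days, a Visit 2 test would close 60% to 70% of the uncovered conception dates; with 7 to 21 days, 50% to 77%. The consequence is a subject-safety matter that probably concerns few women, if any. It does not bear on the immunogenicity endpoints or the SAP. The change is worth making because it is cheap and repeats a test the protocol already uses.

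**What to change.** Add a urine hCG test for women of childbearing potential at Visit 2, before the second vaccination, and give dose 2 only if the result is negative. Three entries change:

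- Section 9.1.8: name the Day 22 test beside those at Day 1 and Day 43.
- Section 9.3.3: add the test to the Day 22 list.
- Appendix A: mark the pregnancy-test row in the Visit 2 pre-vaccination column.

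Section 7.5, item 7, and Section 9.1.9 can stay as they are; a positive result then triggers them in time to withhold dose 2. The cover is partial: on the same assumption, conceptions in roughly the last 10 to 14 days before dose 2 would still be missed.

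The direct cost is one urine strip per woman of childbearing potential, at most 55 because 55 subjects are planned, and the wait for the result before vaccination. No extra visit, blood draw or staff is needed. The administrative cost is a short amendment with IRB approval, a place to record the result in the (e)CRF and, if the consent form has to mention the test, a revised form for signature.

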9.1.9 Pregnancy

If any subject is found to be pregnant during the study she should be withdrawn and any sponsor-supplied drug should be immediately discontinued.

If the pregnancy occurs during administration of active study drug, eg, after Day 1 or within 12 weeks of the last dose of active study drug, the pregnancy should be reported immediately, using a pregnancy notification form, to the contact listed on the attached sheet.

If the female subject agrees to the primary care physician (obstetrician) being informed, the investigator should notify the primary care physician that the subject was participating in a clinical study at the time she became pregnant and provide details of treatment the subject received.

All pregnancies in subjects on active study drug including comparator will be followed up to final outcome, using the pregnancy form. Pregnancies will remain blinded to the study team. The outcome, including any premature termination, must be reported to the sponsor. An evaluation after the birth of the child will also be conducted.

9.1.10 Immunogenicity Evaluation

The SRH and MN antibody titers against influenza virus for immunogenicity evaluation will be measured by the laboratory specified in the procedures. As for blood sampling, 20 mL of blood per sampling will be collected from the forearm vein. The blood sample collected will be used for study-specific endpoint measurements as well as immunogenicity evaluation by a government organization, and also may be used for other exploratory immunogenicity evaluations (see Section 9.4). No genetic testing will be performed using the samples collected in this study.

For the immunogenicity evaluation by a government organization, the protocol and the result report will be prepared by the sponsor or the government organization, separately from the protocol and clinical study report for this study. If other exploratory immunogenicity evaluations are performed, their protocols and result reports should also be prepared.

Detailed procedures for handling and transporting samples are found in separately prepared documented procedures for handling of biological samples for immunogenicity evaluation.

